#### 2.1.2.10.2 Secondary endpoints

##### 2.1.2.10.2.1 Changes in alveolar-arterial oxygen difference (A-aDO2) from baseline to each time point

- (1) Analysis set : FAS
- (2) Analysis item : measured values and changes in A-aDO2 (values at each time point- those at Day1)
- (3) Time point : Day 1, Day 3, Day 5, Day 10, at discontinuation/completion of treatment

(4) Analytical method :

- 1) Summary statistics (number of patients, arithmetic mean, standard deviation, median, minimum, maximum) for measured values and changes will be calculated by treatment group and by time point. In addition, a chart for the mean  $\pm$  standard deviation over time and box-and-whisker plot will be prepared by treatment group.
- 2) Estimated values of the differences between groups, 95% confidence intervals, and p-values (Day 3, Day 5, Day 10) will be calculated using mixed effect model for repeated measures (cLDA method) by time point with the measured values as the response variable, time point, treatment group, and treatment group \* time point as the fixed effects, and patients as the random effect, setting that both groups have the common mean value on Day 1. In addition, estimated values and 95% confidence intervals over time will be prepared by treatment group.
- 3) Estimated values of the differences between groups, 95% confidence intervals, and p-values (Day 5, at discontinuation/completion of treatment) will be calculated using mixed effect model for repeated measures with the measured values and changes as the response variable, baseline values as the covariate, time point (Day 1, Day 5, at discontinuation/completion of treatment), treatment group, treatment group \* time point as the fixed effects, and patients as the random effect. In addition, a chart for the estimated values and 95% confidence intervals over time will be prepared by treatment group.
- 4) The number of patients of whom changes from baseline (Day 1) decreased (improved) by 33% or more and the proportion will be calculated by treatment group and by time point (number of patients, %), and the p-values (Fisher's exact test) will be calculated.

2.1.2.10.2.2 Period from baseline to the day of discharge (days until shifting to Category 7 on a 7-point ordinal scale)

- (1) Analysis set : FAS
- (2) Analysis item : period from baseline to the day of discharge (time point - Day 0)
- (3) Time point : Day 0 to Day 28
- (4) Analytical method :
  - 1) Period from baseline to the day of discharge will be estimated by treatment group using the Kaplan-Meier method, and comparison between groups will be performed as well using the log-rank test with a significance level of 5%. Definitions of events and censoring are presented in Table 2.3.

2.1.2.10.2.3 Period from baseline to shifting to Category 6 or 7 on a 7-point ordinal scale

- (1) Analysis set : FAS
- (2) Analysis item : period to shifting to Category 6 or 7 on a 7-point ordinal scale from baseline (time point - Day 0)
- (3) Time point : Day 0 to Day 28
- (4) Analytical method :
  - 1) Period from baseline to shifting to Category 6 or 7 on a 7-point ordinal scale will be estimated by treatment group using the Kaplan-Meier method, and comparison between groups will be performed as well using the log-rank test with a significance level of 5%. Definitions of events and censoring are presented in Table 2.3.

2.1.2.10.2.4 Rate of shifting to Category 1 or 2 on a 7-point ordinal scale during the period from baseline to Day 10 or Day 28

(1) Analysis set : FAS

(2) Analysis item : rate of shifting to Category 1 or 2 on a 7-point ordinal scale from baseline (time point - Day 0)

(3) Time point : Day 0 to Day 28

(4) Analytical method :

- 1) The number of patients of whom the category has shifted to Category 1 or 2 on a 7-point ordinal scale and the proportion during the period from baseline to Day 10 or Day 28 will be summarized by treatment group and by time point (number of patients, %).
- 2) The p-values (Fisher's exact test) on Day 10 or Day 28 will be calculated for the rate of shifting to Category 1 or 2 on a 7-point ordinal scale during the period from baseline to Day 10 or Day 28.
- 3) Period from baseline to shifting to Category 1 or 2 on a 7-point ordinal scale will be estimated by treatment group using the Kaplan-Meier method, and comparison between groups will be performed as well using the log-rank test with a significance level of 5%. Definitions of events and censoring are presented in Table 2.3.

2.1.2.10.2.5 Changes from baseline in pulmonary inflammatory findings at each time point

(1) Analysis set : FAS

(2) Analysis item : changes from baseline in pulmonary inflammatory findings (each time point - Day 0)

(3) Time point : Day 0, Day 5, at discontinuation/completion of treatment

(4) Analytical method :

- 1) Pulmonary inflammatory findings will be examined according to Section 13.11 "High Resolution Chest CT (HRCT) or Plain Chest CT or Chest X-ray" at the time point specified in Section 2 "Observation/Examination Schedule" of the protocol and the finding results will be classified into 3 categories by the investigator. Then, the number of patients and the proportion in each category will be summarized by treatment group and by time point (number of patients, %).
- 2) Regarding the number of cross sections for which Crazy-paving appearance, Bronchial wall thickening, Subpleural curvilinear shadow, Vascular thickening, Airspace consolidation, Small nodule opacity, Reticular shadow, Plate atelectasis, or AIP/ARDS pattern (DAD pattern) has been found in the specified 9 cross sections each in the left and right side (18 cross sections in total) on chest HRCT, summary statistics (number of patients, arithmetic mean, standard deviation, median, minimum, maximum) for each finding will be calculated by treatment group and by time point. In addition, a chart for mean  $\pm$  standard deviation over time will be prepared by treatment group. Moreover, estimated values of the differences between groups, 95% confidence intervals, and p-values (Day 5, at discontinuation/completion of treatment) will be calculated using mixed effect model for repeated measures with the changes from baseline to each time point as the response variable, baseline values as the covariate, time point, treatment group, and treatment group \* time point as the fixed effects. A chart for changes in the estimated values and 95% confidence intervals over time will be also prepared by treatment group.  
Separately from the above assessment, presence or absence of findings of Lymph node enlargement, Pleural effusion, Pericardial effusion, Pneumothorax, or Pneumomediastinum will be checked in the entire lungs, and the number of patients who have such findings and the proportion will be summarized for each finding by treatment group and by time point (number of patients, %).

3) Assuming normal lung, GGO, or consolidation, summary statistics (number of patients, arithmetic mean, standard deviation, median, minimum, maximum) for the percentage of each volume on chest HRCT against the total lung volume will be calculated. In addition, a chart for mean values  $\pm$  standard deviation over time will be prepared by treatment group. Moreover, estimated values of the differences between groups, 95% confidence intervals, and p-values (Day 5, at discontinuation/completion of treatment) will be calculated using mixed effect model for repeated measures with the changes from baseline to each time point as the response variable, baseline values as the covariate, time point, treatment group, and treatment group\* time point as the fixed effects. A chart for changes in estimated values and 95% confidence intervals over time will be also prepared by treatment group.

Total lung volume	Bilateral lung volume from hilum to periphery excluding trachea and main bronchus (mL)
Normal	CT Value: Volume of the region approximately at -801 HU or lower. *Assuming normal lung
High-density area 1	CT Value: Volume of the region approximately between -800 and -551 HU. *Assuming GGO
High-density area 2	CT Value: Volume of the region approximately at -550 HU or higher *Assuming consolidation

The volume of the following five regions in the entire lungs excluding the trachea and main bronchus will be calculated, and the percentages of those volumes against total lung volume will be calculated. The ranges of CT values for calculation of the volume are as follows.

- Volume\_1 : [-801] HU or lower
- Volume\_2 : [-800 to -601] HU
- Volume\_3 : [-600 to -401] HU
- Volume\_4 : [-400 to -201] HU
- Volume\_5 : [-200] HU or higher

Summary statistics (number of patients, arithmetic mean, standard deviation, median, minimum, maximum) for the changes from baseline in the percentage of above mentioned each Volume will be calculated by treatment group and by time point. In addition, box-and-whisker plots for the changes from baseline to Day 5 will be prepared in each Volume by treatment group. Estimated values of the differences between groups, 95% confidence intervals, and the p-values will be calculated using generalized estimating equations with the changes in percentages of any Volumes from baseline to Day 5 as the response variable, treatment group, categories of Volume and treatment group \* categories of Volume as the fixed effects, and patients as the repeatedly measured correlation group.

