2 Observation and Examination Schedule

Item	Screening	Date of allocation	Observation period ⁵⁾												Discontinuation/ Exit Test ⁶⁾
			Day 0	Day 1	Day 2	Day 3	Day 4	Day 5	Day 6	Day 7	Day 8	Day 9	Day 10	Day 11 ~14	Day 15 ~28
Acceptable window	To Day 0	-2 days ⁷⁾	—	—	—	—	—	+1 day ⁷⁾	—	—	—	—	—	—	+1 day
Informed consent	●														
Medical history/current medical conditions	●														
Subject characteristics	●														
Height and weight	●														
Inclusion and exclusion criteria	●														
Percutaneous oxygen saturation (SpO2)	●														
Allocation		●													
Study drug administration ¹⁾			●	●	●	●	●	●	○	○	○	○	○		
7-point ordinal scale ²⁾			●	●	●	●	●	●	●	●	●	●	●	●	
Oxygen requirement			●	●	●	●	●	●	●	●	●	●	●	●	
Arterial blood gas analysis (PaO2, PaCO2, A-aDO2, others)			● ³⁾					●							●
Inflammatory markers, cytokines			● ³⁾		●		●								●
Chest HRCT or plain chest CT or Chest X-ray			●					●							●
Physical examination			●					●							●
Vital sign			●					●							●
12-lead ECG			●					●							●
Laboratory tests (blood chemistry, hematology and urinalysis)			●					●							●
Pregnancy test (urine or blood sample)			●												
adverse events ⁴⁾				●									●		
Concomitant medication/therapy		●	—									●			

● : Will be performed in all the subjects ○ : Will be performed only in the subjects who continue to receive the study drug after Day 5.

1) Inhalation administration will be started on the morning of Day 1 and performed twice daily (morning, evening) for 5 days, in principle (up to 10 days).

2) Will be evaluated every day during the period between Day 1 and Day 28. Use or no use of a ventilator will be included in this evaluation.

3) Will be performed prior to study drug administration.

4) Only the adverse events that have occurred until Day 14 after the start of study drug administration. may be collected and entered in the electronic case report form. Serious adverse events related to the study drug administration will be collected until Day 28.

- 5) Assessment of efficacy on the 7-point ordinal scale and oxygen requirement will be performed after completion of the second dose (inhalation) of the day.
- 6) Will be performed on the day of discontinuation if study drug administration has been prematurely discontinued before Day 5, or on the day of the last dose in the case that the last day is not Day 5.
- 7) Except 7-point ordinal scale and oxygen requirement.

3 Study Administrative Structure

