5.2.1.2 Changes in alveolar -arterial oxygen gradient (A-aDO₂)

A-aDO₂ will be measured and calculated according to "13.10 Arterial blood-gas analysis (PaO₂, PaCO₂, A-aDO₂, others)" at the timing specified in "2 Observation and Examination Schedule."

Measurement values obtained prior to study drug administration on Day 1 will be used as baseline values, and changes of A-aDO₂ values from baseline will be assessed.

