#### 4.7 SAS Code

- SAS Code for implementing Cox regression model is shown below.

```
ods output ParameterEstimates = [OUTPUT];
proc phreg data = [DATASET];
  class [GROUP] [THERAPY];
  model [TARGET] * [CENSOR FLG](0) = [GROUP] [THERAPY] / rl alpha = 0.05;
run;
```

- SAS Code for implementing MMRM model is shown below.

```
proc mixed data = [DATASET];
  class [SUBJECT] [VISIT] [GROUP];
  model CHG = BASE [VISIT] [GROUP] [VISIT] * [GROUP] /ddfm = KR;
  lsmeans [GROUP]* [VISIT];
  repeated [VISIT]/ subject = [SUBJECT] type = UN;
```

run;

- SAS Code for implementing analysis using generalized estimating equation is shown below.

```
proc genmod data = [DATASET];
  class [SUBJECT] [VOLUME] [GROUP];
  model CHG = [GROUP] [VOLUME] [GROUP]* [VOLUME] ;
  lsmeans [GROUP]* [VOLUME];
  repeated subject = [SUBJECT] type = UN or CS;
run;
```

- SAS Code for implementing analysis using MMRM model (cLDA method) is shown below.

\* The coefficient of Estimate must be changed to suit the data.

\*The value of DIF3, DIF5, and DIF10 in the active group is 1 at each time point, otherwise 0.

```
proc mixed data = [DATASET] order = internal;
  class AVISITN(ref = "1") USUBJID;
  model AVAL_ = AVISITN DIF3 DIF5 DIF10/noint s ddfm = kr;
  random USUBJID;
  /* difference between groups in each time point*/
  estimate "Diff (NPC-26 - Placebo) Day3" DIF3 1 /cl;
  estimate "Diff (NPC-26 - Placebo) Day5" DIF5 1 /cl;
  estimate "Diff (NPC-26 - Placebo) Day10" DIF10 1 /cl;
  /* Mean CHG in each time point in each group */
  estimate "LSMean of Change from BL (Placebo) Day3" AVISITN 1 0 0 -1 /cl;
  estimate "LSMean of Change from BL (Placebo) Day5" AVISITN 0 1 0 -1 /cl;
  estimate "LSMean of Change from BL (Placebo) Day10" AVISITN 0 0 1 -1 /cl;
  estimate "LSMean of Change from BL (NPC-26) Day3" AVISITN 1 0 0 -1 DIF3 1 /cl;
  estimate "LSMean of Change from BL (NPC-26) Day5" AVISITN 0 1 0 -1 DIF5 1 /cl;
  estimate "LSMean of Change from BL (NPC-26) Day10" AVISITN 0 0 1 -1 DIF10 1 /cl;
  /*Mean AVAL in each time point in each group */
  estimate "LSMean (Placebo) Day1" AVISITN 0 0 0 1 /cl;
  estimate "LSMean (Placebo) Day3" AVISITN 1 0 0 0 /cl;
  estimate "LSMean (Placebo) Day5" AVISITN 0 1 0 0 /cl;
  estimate "LSMean (Placebo) Day10" AVISITN 0 0 1 0 /cl;
  estimate "LSMean (NPC-26) Day1" AVISITN 0 0 0 1 /cl; *This is same as in common with
Placebo;
  estimate "LSMean (NPC-26) Day3" AVISITN 1 0 0 0 DIF3 1 /cl;
  estimate "LSMean (NPC-26) Day5" AVISITN 0 1 0 0 DIF5 1 /cl;

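### SAP A-aDO2 method 3) uses Day 1 both as the baseline covariate and as a response time point, so the model either has no valid fit or understates its error

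*SAP*

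**What the plan says.** Both documents take Day 1 as the A-aDO2 baseline. Protocol 5.2.1.2: "Measurement values obtained prior to study drug administration on Day 1 will be used as baseline values". SAP 2.1.2.10.2.1 defines change as "values at each time point- those at Day1", and its method 4) also treats Day 1 as baseline.

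Method 3) of that SAP section is a mixed model "with the measured values and changes as the response variable, baseline values as the covariate". Its time factor is "time point (Day 1, Day 5, at discontinuation/completion of treatment", and patients enter as a random effect. Estimates and p-values are requested for Day 5 and for discontinuation/completion.

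The matching code in SAP 4.7 is "model CHG = BASE [VISIT] [GROUP] [VISIT] * [GROUP] /ddfm = KR", with "repeated [VISIT]/ subject = [SUBJECT] type = UN". It has one baseline slope common to all visits, an unstructured covariance instead of a random patient effect, and no step that drops Day 1 rows.

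Method 2) is a separate cLDA model. Day 1 is a response there, with a mean common to both groups and no baseline covariate. It reports Days 3, 5 and 10.

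Note 6 of the protocol's observation schedule places the exit test on the day of discontinuation if that is before Day 5, or "on the day of the last dose in the case that the last day is not Day 5".

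**The concern.** A baseline-adjusted model should have only post-baseline values as responses. Here Day 1 stands on both sides of the equation, so one third of the response rows carry no information and no error. What follows depends on the covariance used, and the SAP gives two.

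A-aDO2 change is the first-listed secondary endpoint, and the protocol names two contrasts for it: Day 5 and end of administration. The cLDA model covers Day 5 only. The end-of-administration difference, interval and p-value come from method 3) alone. Since SAP 2.1.2.13 makes no multiplicity adjustment, each nominal 5% p-value will be read on its own.

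A further problem affects the completion level. A patient whose last dose is on Day 5 has no separate exit test, so for that patient the level either repeats the Day 5 value or is empty.

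**Working it through.** The documents give no figure for the A-aDO2 model. Their only design figure, 82.1% power for the primary log-rank test (Protocol 18), reproduces at 82.4% and plays no part here. Group sizes of 40 and 20 come from the same section, and the two-sided 5% level from SAP 2.1.2.12. All A-aDO2 means, SDs and correlations below are assumptions.

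**1. Day 1 rows.** Change at Day 1 = Day 1 value − Day 1 value = 0 for every patient, so its variance is 0. For measured values the response equals the covariate. The two fits are algebraically the same, with the slope shifted by 1.

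**2. Unstructured covariance (SAP 4.7 code).** A slope of 0 with zero Day 1 means fits all 60 Day 1 rows exactly. Those rows determine three parameters: the Day 1 intercept, the Day 1 group effect and the slope. The restricted likelihood therefore contains (60 − 3) × ln(Day 1 variance). Each 100-fold cut in that variance should lower −2REML by 57 × ln(100) = 262.5. In a simulated data set, with Day 1 variance set to 1, 0.01, 0.0001 and 0.000001, −2REML was 778.0, 515.5, 253.0 and −9.5. That is a fall of 262.5 each time, without limit. The baseline slope went to 0 (−0.36 without Day 1), and the Day 5 difference moved from −2.73 to −4.47. In the limit the model is an unadjusted change-score comparison. Over 600 null trials in each of three scenarios, its Day 5 SE was 4.58 against 4.33 for the proper unstructured fit, 3.17 against 2.96, and 5.36 against 4.71, which is 6–14% larger. Type I error stayed at 4.5–5.5%.

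**3. Random patient effect (SAP text).** This structure assumes the same variance at every time point.

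- Slope: the true slope is 0 at Day 1 and b at the other two levels, so the common slope becomes (0 + b + b)/3 = 2b/3. In the first scenario it went from −0.431 to −0.287.
- SE, first scenario: the model without Day 1 has SE 4.71, so its pooled variance is 4.71² / (1/40 + 1/20) = 295.8. With baseline SD 15, slope misfit contributes (2/3 × 0.431 × 15)² = 18.6 at Day 1 and (1/3 × 0.431 × 15)² = 4.6 at each later level. The new pooled variance is (18.6 + 2 × 300.4)/3 = 206.5, giving SE = √(206.5 × 0.075) = 3.94. The simulation gave 3.92.

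Null simulations, 600 trials per row, Monte Carlo error about 1 percentage point:

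| Correlations (Day 1–5, Day 1–end, Day 5–end); SDs | Model SE, Day 1 in / out | Actual SD, Day 1 in: Day 5 / end | Type I, Day 1 in: Day 5 / end | Type I, Day 1 out: Day 5 / end |
|---|---|---|---|---|
| 0.5, 0.4, 0.7; 15, 18, 20 | 3.92 / 4.71 | 4.15 / 4.99 | 6.2% / 13.2% | 2.7% / 6.0% |
| 0.7, 0.6, 0.8; 15, 15, 15 | 2.64 / 3.13 | 2.85 / 3.35 | 5.5% / 11.7% | 2.8% / 6.8% |
| 0.3, 0.3, 0.9; 15, 18, 20 | 4.24 / 4.99 | 4.74 / 5.23 | 9.3% / 10.8% | 2.8% / 5.8% |

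The SE is 15–17% smaller with Day 1 in than with it out. Averaged over the two time points, type I error is about 9–10% with Day 1 in and 4–5% with it out. The unstructured model without Day 1 gave 3.8–5.7%.

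**4. Other assumptions.** Baseline mean 45 and SD 15, Day 5 residual SD 10, 70% of end-of-treatment values equal to Day 5, baseline slope 0.3–0.8, 1,500 trials per setting. Type I error was 6.1–9.7% with Day 1 in and 5.1% with it out; a repeat run gave 7.7–10.9% and 4.2–5.0%. At slope 0.8 the mean SE was 2.35 (2.28 on repeat), against an actual SD of 2.74–2.80. The expected SD is 10 × √0.075 = 2.74.

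**The case against.** The strongest reply is that the two harms never occur together. The only code with a baseline covariate is unstructured, and there the limiting analysis is valid, only less precise; an unbounded likelihood would probably show when the program is run. Results are requested only for Day 5 and completion, and the code is a generic template that names no visits. If it is run on post-baseline rows, the problem disappears. The endpoint is secondary, and Day 5 is also tested by the unaffected cLDA model.

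Much of this stands. Optimistic p-values belong to the random-effect reading, lost adjustment or a failed fit to the unstructured one. But the SAP explicitly lists Day 1 as a level, so dropping it would be an unrecorded departure. Because text and code disagree on covariance, the result would depend on a choice the SAP does not settle. The cLDA model does not give the end-of-administration contrast.

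On patients who finish on Day 5, SAP 2.1.2.14 (5) says blood-gas data at a completion falling on Day 1, 3, 5 or 10 count as that day's data. It does not make clear whether the completion level is then also filled. Item (6) refers to further rules that are not in the text available here, so this part cannot be fully judged.

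**Conclusion.** Method 3) is wrong as written and should be corrected. The zero Day 1 variance, the unbounded likelihood under the unstructured covariance and the forced baseline slope follow from the SAP's own definitions and need no assumptions. The size of the harm under the random patient effect does rest on assumed SDs, correlations and overlap between Day 5 and completion. Across the settings tried, type I error was 5.5–10.9% at Day 5 and 10.8–13.2% at end of treatment. The primary endpoint and the cLDA analysis are not affected.

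**What to change.** - In method 3), delete Day 1 from the time factor, keep it as the covariate, and fit Day 5 and end of administration as the responses.
- State one covariance structure and make text and code agree. Unstructured held its level once Day 1 was removed. The random patient effect averaged about 5% but was uneven between the two time points.
- Preferably add a baseline by time point term, so that each time point has its own slope.
- State what the end-of-administration value is for patients who finish on Day 5. If it repeats Day 5, analyse end of administration in its own ANCOVA.
- Say once that baseline-adjusted repeated-measures models use post-baseline responses only. The models in SAP 2.1.2.10.2.5 to 2.1.2.10.2.7 do not list their levels, although their time-point lists include the baseline visit. Day 1 stays a response in the cLDA models.

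The cost is a line or two of SAP text and a data filter, plus the revised SAP and the statement of timing, reason and impact that Protocol 17.6 requires. No new data are needed.

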#### 2.1.2.10.2.6 Changes from baseline in arterial blood gas values (PaO2, PaCO2, pH) to each time point.

(1) Analysis set : FAS

(2) Analysis item : measured values and changes in arterial blood gas (each time point - Day 1)

(3) Time point : Day 1, Day 3, Day 5, Day10, at discontinuation/completion of treatment

(4) Analytical method :

- 1) Summary statistics (number of patients, arithmetic mean, standard deviation, median, minimum, maximum) for measured values of arterial blood gas and changes from baseline to each time point will be calculated by treatment group and by time point. In addition, a chart for changes in the mean  $\pm$  standard deviation over time will be prepared by treatment group.
- 2) Estimated values of the differences between groups, 95% confidence intervals, and the p-values (Day 3, Day 5, Day 10) will be calculated using mixed effect model for repeated measures (cLDA method) with the measured values as the response variable, time point, treatment group, and treatment group \* time point as the fixed effects, and the patients as the random effect, setting that both groups have the common mean value on Day 1. In addition, a chart for changes in the estimated values and 95% confidence intervals over time will be prepared by treatment group.
- 3) Estimated values of the differences between groups, 95% confidence intervals, and the p-values (Day5, at discontinuation/completion) will be calculated using mixed effect model for repeated measures with the measured values of arterial blood gas and the changes from baseline to each time point as the response variables, baseline values as the covariate, time point, treatment group, and treatment group \* time point as the fixed effects. In addition, a chart for estimated values and 95% confidence intervals over time will be prepared by treatment group.
- 4) The number of patients and the proportion according to implementation status of arterial blood gas analysis (implemented, implemented while supplementing oxygen because supplementing oxygen could not be suspended, not implemented, not implemented because supplementing oxygen could not be suspended) will be summarized by treatment group (number of patients, %).
- 5) A list of outliers in  $\text{PaO}_2$  values on Smirnov-Globus test (significance level of 0.1) in any of the treatment groups will be prepared by time point.

